6.2 Data Security

Describe the steps that will be taken secure the data (e.g., training, authorization of access, password protection, encryption, physical controls, certificates of confidentiality, and separation of identifiers and data) during storage, use, and transmission.

As noted above, to assure confidentiality, anonymous data and recordings of therapy sessions will be secured in a database management system, password protected files, and in secure file cabinets. Data collection forms, databases, and recordings will not include identifiers other than a study ID code. We will include all three levels of security: password protection, computer or file cabinet locks, and a locked office. Participants' encrypted cognitive task data will be housed on a secure server "using Secure Sockets Layer (SSL), the same technology used by online shopping and banking web sites to protect sensitive information transmitted over the web"

6.3 Data and Safety Monitoring

A. Periodic Data Evaluation

Describe the plan to periodically evaluate the data collected regarding both harms and benefits to determine whether subjects remain safe. The plan might include establishing a data monitoring committee and a plan for reporting data monitoring committee findings to the IRB and the sponsor.

Version Number: 15, 2/2/2022 Protocol Number: Pro20190016877

PI Name: [name]

Protocol Title: Mindfulness Oriented Recovery Enhancement (MORE) as an Adjunct to Methadone Treatment RESERVED FOR IRB STAMP
DO NOT MODIFY THIS SPACE

The Data and Safety Monitoring Board (DSMB) will meet every 6 months to monitor and evaluate the safety of participants throughout the course of the research study. The DSMB will:

- Assess the performance of the study with respect to participant recruitment, retention and follow-up, protocol adherence, and data quality and completeness.
- Monitor interim data regarding the safety of the study regimes.
- Review and consider any protocol modifications or ancillary studies proposed by study investigators after the main trial begins to ensure that these do not negatively impact on the main trial.
- Advise the Institutional Review Board as to whether the protocol should continue as scheduled or undergo a modification due to a finding from the monitoring process.

B. Type of Data Evaluated

Include what data are reviewed, including safety data, untoward events, and efficacy data.

The study investigators and the DSMB will be responsible for data safety and monitoring. The DSMB and the investigators will monitor the cumulative safety data during the period when participants are in the study. They will: 1) assess the performance of the study with respect to participant recruitment, retention and follow-up, protocol adherence, and data quality and completeness, to help ensure the likelihood of successful and timely trial completion; 2) monitor interim data regarding the safety of the study regimens; 3) review and consider any protocol modifications by the study investigators after the trial begins to ensure that these do not negatively impact on the study; and 4) advise the Institutional Review Board and NIH as to whether the protocol should continue as scheduled or undergo a modification due to a finding from the monitoring process.

C. Collection of Safety Information

Explain how the safety information will be collected (e.g., with case report forms, at study visits, by telephone calls with participants).

Safety information will be collected during participant's assessments, telephone calls with participants, conversations with clinic staff, and MORE group sessions.

D. Frequency of Data Collection

The frequency of data collection, including when safety data collection starts.

Safety data collection will begin with collection of the first baseline assessment and continue through the end of the follow-up data collection period (about 2-years total). In addition to using assessment data to monitor safety, study clinicians will record any adverse events that they become aware of during MORE group sessions and study Investigators will ask NBCC, JSAS, and the Lennard Clinic personnel, with participant consent, to notify the research team should they become aware that any study participant has been hospitalized or experienced any other adverse event. Such notifications will be requested throughout the study period. All adverse events will be recorded on spreadsheets and will include details of the adverse event and whether or not it was study-related. Numbers and types of events and other quantifiable event details will be entered into a database for analysis.

E. Reviewer of Data

Who will review the data?

The DSMB will meet every six months to monitor the cumulative safety data during the period when participants are in the study. The DSMB will monitor the study according to the guidelines specified in the study protocol and the operating procedures established at the initial DSMB meeting, unless the DSMB

27

Version Number: 15, 2/2/2022 Protocol Number: Pro20190016877

PI Name: [name]

Protocol Title: Mindfulness Oriented Recovery Enhancement (MORE) as an Adjunct to Methadone Treatment RESERVED FOR IRB STAMP
DO NOT MODIFY THIS SPACE

determines during the course of the trial that modification of the guidelines is in the best interest of the study and its participants. Such a decision may be based on new information that emerges during the course of the study (e.g., publication of the results of a similar study), realization of inappropriate initial study assumptions, or the occurrence of an unanticipated scenario. Considering the minimal risk nature of the intervention, we do not anticipate any serious adverse events that could trigger the immediate suspension of the research. However, the Investigators and the DSMB will monitor and evaluate the safety of participants throughout the course of the research study. The Independent Monitors will advise the Investigators and IRB as to whether the protocol should continue as scheduled, undergo a modification, or halt study activities due to a finding from the monitoring process. An interim analysis of the data may be conducted when 50% of the sample is accrued. If the results show statistically overwhelming significant differences between groups, the DSMB will consider the clinical meaning of the results and determine whether the study should be stopped.

F. Schedule of Review of Cumulative Data

The frequency or periodicity of review of cumulative data.

Under supervision of the investigators, a Research Assistant or the Study Coordinator will conduct monthly descriptive summaries on all data to ensure their accuracy. This will not involve completing any statistical comparisons. If problems are noted in data entry (e.g., out of range values, missing values), the Research Assistant and the investigators will investigate the root cause, and solutions to rectify the problem.

G. Tests for Safety Data

The statistical tests for analyzing the safety data to determine whether harm is occurring.

Basic statistical tests, including frequency distributions, Anovas and t-tests, will be carried out, if necessary, to compare the control and intervention groups on numbers and types of adverse events within specific time frames in order to insure the safety of the intervention.

H. Suspension of Research

Any conditions that trigger an immediate suspension of the research.

Considering the minimal risk nature of the intervention, we do not anticipate any serious adverse events that could trigger the immediate suspension of the research.

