in-person. Participants will be asked to sign the electronic consent form on Qualtrics or REDCap, mail a signed paper version back to the research assistant, or drop off a signed paper version to their clinic for research staff to pick up. Alternatively, consenting maybe be done in-person. Participants will also keep a copy of the consent for their records.

Participants randomized to the MORE condition will participate in eight, weekly, two-hour online group sessions led by a clinic or study counselor. Each session will contain 5 to 9 participants and will be conducted online through secure video or phone conferencing. If a participant is unable to join the MORE session through video conference due to technical difficulties at the time of the session, the participant will be instructed to join the session by phone or the participant may go to their clinic and a research or clinic staff member can help them access the intervention through their tablet or a computer. Attendance at each session and reasons for missing sessions will be recorded. Participants randomized to the control condition will continue receiving treatment as usual at their clinic.

All study participants will partake in a total of three interviews lasting up to 120 minutes occurring at baseline, 8-, and 16-weeks (week 1 will be considered the week of the first MORE group session) by video or phone conferencing or in-person. If more than 3 months since baseline survey was administered from start of group (study intervention), clients will be asked to do another baseline survey. Each participant will also have a urine or saliva sample collected during each assessment. This is required to verify self-report of drug use. Due to social desirability, it is common for people to not accurately report drug use; therefore, biochemical verification is the gold standard measure of drug use. Participants will be mailed a urine or saliva test prior to the interview.

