4.9 Risks to Subjects

A. Description of Subject Risk

This study involves accepted forms of treatment and assessment. Risks to subjects are minimal. The main risk associated with the study is discomfort related to talking about personal issues in study assessments and group sessions. However, participants do not have to talk about anything they do not want to. Loss of confidentiality is a risk. However, group participants will be informed about the importance of confidentiality and study staff will be trained to protect participant confidentiality. While we are not actively recruiting participants with an existing psychological disorder, it is possible we enroll individuals who we subsequently find to be suicidal or have other mental health problems. Personal information may be disclosed to a participant's clinic counselor, program director, or other public safety of healthcare personnel if study staff believes, based upon information reported during intervention sessions or through research assessments, that a participant may harm himself or herself or others. Protocols have been developed to manage unexpected emergencies involving individuals with mental health problems, as well as to manage risks associated with participant discomfort and loss of confidentiality. If the study staff determine that the participant is a harm to him/herself or others to the extent that, based on the implementation of the protocol, it is a new or worsening symptom, it will be considered an adverse event. If the research staff determines that loss of confidentiality is required to protect the individual or others, the event will be reported to the IRB and NIH as a serious adverse event.

20

B. Procedures for Risks to Embryo, Fetus, and/or Pregnant Subjects

N/A

C. Risks to Non-Subjects

N/A

Version Number: 15, 2/2/2022 Protocol Number: Pro20190016877

PI Name: [name]

Protocol Title: Mindfulness Oriented Recovery Enhancement (MORE) as an Adjunct to Methadone Treatment RESERVED FOR IRB STAMP
DO NOT MODIFY THIS SPACE

D. Assessment of Social Behavior Considerations

Reasonably Foreseeable Risks

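### Adverse events heard in MORE sessions, a source that TAU lacks, enter the between-arm safety comparison, so an excess in MORE would be ambiguous

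*Combined protocol and SAP*

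**What the plan says.** Section 6.3 C lists the sources of safety data: "Safety information will be collected during participant's assessments, telephone calls with participants, conversations with clinic staff, and MORE group sessions". The first three can reach any participant; only the MORE arm attends the fourth. Section 6.3 D repeats the session source ("study clinicians will record any adverse events that they become aware of during MORE group sessions") and adds a route that covers both arms, in which clinic personnel are asked, with participant consent, to "notify the research team should they become aware that any study participant has been hospitalized or experienced any other adverse event". The adverse-event record is described as holding event details and study-relatedness; the source of detection is not mentioned.

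Section 1.3 A gives MORE "eight, weekly, two-hour online group sessions led by a clinic or study counselor". For the other arm it says: "Participants randomized to the control condition will continue receiving treatment as usual at their clinic". Both arms have "a total of three interviews lasting up to 120 minutes occurring at baseline, 8-, and 16-weeks".

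Section 6.3 G, on judging whether harm is occurring, provides for frequency distributions, ANOVAs and t-tests, if necessary, "to compare the control and intervention groups on numbers and types of adverse events within specific time frames".

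**The concern.** A count of adverse events measures both how often events happen and how often the study hears of them. Here the second part differs by arm. MORE participants meet a counselor weekly for eight weeks, and what is said there goes on the log. No matching study contact is described for TAU.

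Nothing found in the plan limits the 6.3 G comparison to sources open to both arms, requires the source to be logged, or provides a common adverse-event question on the same schedule in both arms. The session source is not confined to trivial complaints. Section 4.9 provides for action on risk of harm to self or others "based upon information reported during intervention sessions or through research assessments", counts new or worsening risk of this kind as an adverse event, and treats it as serious when confidentiality has to be broken.

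At stake is how the investigators and the DSMB read an apparent excess in MORE: as harm, or as closer listening. A true safety advantage of MORE could also be partly hidden.

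**Working it through.** The plan states no adverse-event rate, capture rate or safety power, so there is no figure to reproduce. The contact and timing inputs come from section 1.3 A; the capture rates are assumptions.

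**Contact in each arm**
- MORE sessions: 8 × 2 h = 16 h.
- Post-baseline interviews, both arms: 2 × up to 2 h = up to 4 h.
- Scheduled study contact after baseline: up to 16 + 4 = 20 h in MORE against up to 4 h in TAU, a ratio of 5.

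Timeline follow-back contacts, made as needed and at most weekly in both arms, are not counted. The ratio shows the asymmetry of opportunity; it does not measure bias.

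**Recorded ratio when true rates are equal**

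Let c be the share of events captured by sources open to both arms, s the share of the remainder heard in sessions, and w the share of events that can surface in sessions at all.

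Recorded ratio MORE:TAU = [c + (1 − c) × w × s] / c

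This exceeds 1 whenever c < 1 and w × s > 0. If events are spread evenly over 16 weeks and only those in the session weeks can surface there, w = 8/16 = 0.5. If all can, w = 1.

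| | c = 0.8, s = 0.2 | c = 0.5, s = 0.4 |
|---|---|---|
| w = 0.5 | (0.8 + 0.2 × 0.5 × 0.2)/0.8 = 0.82/0.80 = 1.025 | (0.5 + 0.5 × 0.5 × 0.4)/0.5 = 0.60/0.50 = 1.20 |
| w = 1 | (0.8 + 0.2 × 0.2)/0.8 = 0.84/0.80 = 1.05 | (0.5 + 0.5 × 0.4)/0.5 = 0.70/0.50 = 1.40 |

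Outside that range, with w = 1: c = 0.9 and s = 0.2 give 0.92/0.90 = 1.02; c = 0.4 and s = 0.5 give 0.70/0.40 = 1.75.

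**Effect on a t-test**

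This used 4,000 simulated Poisson trials per setting, 92 participants per arm (the maximum in section 1.5), equal true rates of 0.2 to 1.0 events per participant, and a two-sided 5% test. With c = 0.6 and w × s = 0.25 the ratio is 0.70/0.60 = 1.17. A significant result against MORE then appears in 5% to 14% of trials, against a nominal 2.5%. Over c = 0.4 to 0.8 and w × s = 0.1 to 0.5, the figure runs from about 3% to 78%. The top needs the least favourable value of all three inputs together.

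**Effect of restricting to shared sources**

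Under equal true rates the expected ratio is c/c = 1.00, provided an event heard both in a session and through a shared source stays in. If the log kept only the first source, and a fraction f of the events that shared sources would have captured were first heard in a session, the ratio would be 1 − f: 0.80 at f = 0.2 and 0.60 at f = 0.4. That is a bias in the opposite direction, so the log must hold every source.

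**The case against.** The strongest reply is that unequal contact is inherent in comparing group therapy with usual care, and that little hangs on it here. The 6.3 G tests are to be run only if necessary. They look at types and time windows as well as numbers, so an excess confined to the session weeks would be partly visible. The intervention is described as minimal risk, and the error is on the side of caution. Shared detection may also be dense: regular clinic attendance and counselling, clinic notification throughout the study, follow-back calls and two follow-up interviews. Hospitalisations would probably be found anyway. All of this stands, and it limits the size and the priority of the point. It does not remove the point: the shared routes raise capture in both arms, and the session source remains an addition in one arm only.

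A reader might infer that the safety comparison could not be interpreted in either direction. The documents do not support that. The extra source can only add recorded events in MORE, so an equal or lower count in MORE would be reassuring despite the closer listening.

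A reader might also infer that the DSMB would act on an artefact. No numerical safety boundary is tied to these tests, and the DSMB would know that MORE has sessions. Section 6.3 E provides for a possible interim analysis at 50% accrual and asks the DSMB to consider clinical meaning before any decision to stop. Its operating procedures are not in these documents.

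A last objection concerns the remedy: a comparison limited to shared sources would drop harms that arise in the sessions, and section 4.9 names discomfort there as part of the main risk. That is correct, and it is why the restricted comparison should not stand alone.

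**Conclusion.** The point holds as a one-directional detection bias. Followed as written, the plan tends to record more events in MORE than in TAU when true rates are equal, so an excess in MORE could not be read as harm without knowing how the events were found.

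The size cannot be derived from the documents. Under assumed shared capture of 50-80% and session capture of 20-40% of the remainder, the recorded ratio is about 1.03 to 1.20 if only events in the session weeks can surface in sessions, and 1.05 to 1.40 if all can. Incomplete attendance would lower it. It would be small if shared sources already find most events.

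The comparison is conditional and safety is not the primary outcome. This is a cheap improvement, not a flaw that threatens the trial's main conclusion.

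**What to change.** 1. **Adverse-event log (6.3 D).** Record every source that detected each event, not only the first.
2. **Interviews (1.3 A, 6.3 C).** Ask the same adverse-event question of both arms at the existing 8- and 16-week interviews. Events first heard in a session then have the same scheduled chance of being found through a shared source.
3. **Comparison (6.3 G).** Report two between-arm comparisons side by side: (a) events detected by at least one source open to both arms (assessments, telephone calls, clinic notification), keeping those also heard in a session; and (b) all events.
4. **DSMB listing.** List separately the events found only in MORE sessions, so that session-related harms stay visible.

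The cost is a few extra log entries, one question at two interviews that already take place, and slightly fewer events in the shared-source comparison. No visit, sample size or treatment procedure changes.

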1.3 Research Design and Methods

This study is a 2-arm individually randomized controlled trial design in which outcomes of MMT patients randomized to MORE, delivered remotely, by secure phone or video conferencing, are compared to outcomes of those randomized to treatment as usual (TAU). In the study we will randomize MMT patients with chronic pain to MORE or TAU. This study phase will conduct a clinical trial to assess MORE efficacy and to explore factors impacting the efficacy of MORE on opioid use outcomes. Participants with pain who are receiving MMT for an opioid use disorder (OUD) will be recruited from the New Brunswick Counseling Center (NBCC), Burlington Comprehensive Counseling, the Lennard Clinic, and Jersey Shore Addiction Services (JSAS).

A. Describe, in order of occurrence, all research procedures being performed, when and where they are performed, and by whom (including procedures being performed to monitor subjects for safety or minimize risks).

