New Brunswick Counseling Center (NBCC) at [name]. [name] has conducted several research studies at NBCC, and the clinic is extremely enthusiastic about being a research site for this project (see attached letter). The New Brunswick Counseling Center (NBCC) provides comprehensive, evidence-based, individualized, substance abuse treatment services. NBCC's staff includes a multidisciplinary team of medical, psychological, social work, and substance abuse professionals. NBCC currently approximately 500 patients receiving methadone maintenance treatment, and, in the past year, almost 90% of admissions to the center reported current cigarette smoking. The clinic is in central New Brunswick, NJ, within walking distance from where the Division of Addiction Psychiatry offices are located, making this location ideal for patient recruitment and collaboration. Office and group counseling space is available at the NBCC for the research staff to see study participants, if necessary.

Burlington Comprehensive Counseling (under the same leadership as NBCC) [name]. Burlington Comprehensive Counseling provides comprehensive, evidence-based, integrated mental health and substance abuse treatment services. Services are individualized and provided in an outpatient setting for prevention, early intervention, and treatment of people with mental health, substance use and/or co-occurring disorders. Program provides access to substance abuse and mental health services addressing the bio-psychosocial consequences associated with substance use and dependence.

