4.0 Research Data Source/s

4.1 Primary Data-Subjects and Specimens

4.2 Subject Selection and Enrollment Considerations

A. Recruitment Details

Up to 184 participants will be recruited from the New Brunswick Counseling Center (NBCC), Burlington Comprehensive Counseling, the Lennard Clinic, Jersey Shore Addiction Services (JSAS). MMT clinic staff will be asked to refer appropriate patients to the study. Clinic patients who are interested and potentially

16

Version Number: 15, 2/2/2022 Protocol Number: Pro20190016877

Pl Name: [name]

Protocol Title: Mindfulness Oriented Recovery Enhancement (MORE) as an Adjunct to Methadone Treatment RESERVED FOR IRB STAMP
DO NOT MODIFY THIS SPACE

eligible for the study will be provided with the study phone number to reach the research staff. Alternatively, clinic staff will get permission from potentially eligible and interested individuals for the clinic to provide contact information to study staff for study staff to reach out to them for study recruitment by phone. Clinic staff will be informed of the eligibility criteria for the study and will be asked to not refer patients that they know are actively suicidal or psychotic. Also, flyers will be posted in dosing areas and the waiting rooms of all participating clinics. Research assistants (RAs) may recruit patients in clinic waiting areas, if and when feasible. Patients expressing interest in the research will be given detailed study information by the RA and initial screening for study eligibility will be conducted over the phone, through video conference, or in-person.

B. Source of Subjects

Participants will be recruited from the New Brunswick Counseling Center (NBCC), Burlington Comprehensive Counseling, the Lennard Clinic, and Jersey Shore Addiction Services.

C. Method to Identify Potential Subjects

Clinic staff will be informed of the eligibility criteria for the study and will be asked to not refer patients that they know are actively suicidal or psychotic. Patients expressing interest in the research will be given detailed study information by the RA and initial screening for study eligibility will be conducted over the phone, through video conference, or in-person. Also, flyers will be posted in dosing areas and the waiting rooms of all participating clinics.

D. Subject Screening

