4.5 Number of Subjects

A. Total Number of Subjects

Total number of subjects to be accrued is up to 184.

B. Total Number of Subjects If Multicenter Study

N/A

C. Require Number of Subjects to Complete Research

N/A

E. Feasibility of Recruiting

NBCC serves approximately 500 MMT clients per year, the Lennard Clinic serves approximately 1000 MMT clients at two sites, and JSAS serves about 700. Based on the prior research studies conducted at these clinics and the high amount of clients served, there are no anticipated problems in recruiting ample subjects. Additional sites will be added to the study if necessary if recruitment targets are not being met.

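### Burlington recruits participants but is not among the clinics asked to report adverse events, so capture there may be less complete

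*Combined protocol and SAP*

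**What the plan says.** Section 4.2 B gives the source of participants: "Participants will be recruited from the New Brunswick Counseling Center (NBCC), Burlington Comprehensive Counseling, the Lennard Clinic, and Jersey Shore Addiction Services". The opening of 1.3, its account of recruitment procedures (1.3 A), and 4.2 A and 4.2 E name the same four organisations. Section 2.2 gives Burlington its own entry and notes that it shares leadership with NBCC.

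Section 6.3 C lists how safety information is gathered at any clinic: participant assessments, "telephone calls with participants, conversations with clinic staff, and MORE group sessions".

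Section 6.3 D adds a standing route through the clinics. It says that "study Investigators will ask NBCC, JSAS, and the Lennard Clinic personnel", subject to participant consent, "to notify the research team should they become aware that any study participant has been hospitalized or experienced any other adverse event". The request is to be made throughout the study. Burlington is not in that list, and nothing else in the published text makes the same request of its staff.

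Section 4.5 E, on feasibility, has the same three names: "NBCC serves approximately 500 MMT clients per year, the Lennard Clinic serves approximately 1000 MMT clients at two sites, and JSAS serves about 700".

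**The concern.** The request in 6.3 D is the one safety route that both sets a standing expectation and does not need the participant to respond. A participant who is in hospital, has left treatment or has stopped answering calls is the one whom interviews and calls are most likely to miss, and clinic staff are well placed to hear of such an event. If one recruiting clinic is not asked, ascertainment may differ between clinics for reasons unrelated to the intervention.

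Two uses of the data are touched. The DSMB reviews cumulative safety data every six months (6.3 A and E), and 6.3 G provides for comparing the arms on numbers and types of adverse events if necessary. Both work best when events are sought in the same way at every clinic and in both arms.

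**Working it through.** No figure in the plan bears on this point, so the check is a comparison of lists and then of routes.

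**Step 1. Which clinics are named where.**

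| Section | Purpose of the list | NBCC | Lennard | JSAS | Burlington |
|---|---|---|---|---|---|
| 1.3, opening | recruiting clinics | yes | yes | yes | yes |
| 1.3 A | recruitment procedures | yes | yes | yes | yes |
| 2.2 | facilities | yes | yes | yes | yes |
| 4.2 A and B | recruitment and source of participants | yes | yes | yes | yes |
| 4.2 E | flyers | yes | yes | yes | yes |
| 4.5 E | feasibility | yes | yes | yes | **no** |
| 6.3 D | adverse-event request | yes | yes | yes | **no** |

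Four organisations recruit and three are asked to report: 4 − 3 = 1, and the one missing is Burlington. Where Burlington appears, it is named alongside NBCC, so NBCC is not used in those lists as a label for both.

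**Step 2. Which safety routes remain for a Burlington participant.**

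| Route | TAU | MORE | Needs the participant to take part? |
|---|---|---|---|
| Assessments at baseline, 8 and 16 weeks | yes | yes | yes |
| Telephone calls with participants | yes | yes | yes |
| Conversations with clinic staff (6.3 C) | yes | yes | no, but no standing request |
| Eight weekly MORE sessions | no | yes | yes |
| Standing request to clinic staff (6.3 D) | not named | not named | no |

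Contact prompted by the weekly review of EMA completion (1.9) also occurs between visits, but its stated aim is to recover missing drug-use data. An adverse event might surface there incidentally.

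**Step 3. What follows by arm.** Participants are randomised within site (4.3), so the omission applies to both arms at Burlington. The remaining routes are not equal, because only the MORE arm has group sessions, and only for eight of the 16 weeks. The 6.3 D request would work alike in both arms. Without it, any differential loss at Burlington would more likely fall on TAU, which would make MORE look relatively less safe. This is a possible direction, not an estimate.

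**Step 4. Size.** Let *f* be Burlington's share of participants and *m* the probability that a Burlington event is missed for want of the request. If event rates are equal across clinics, the share of all events lost is *f* × *m*, which lies between 0 and *f*. The documents give neither quantity, and neither 2.2 nor 4.5 states a methadone census for Burlington from which to guess *f*. For scale only: 4.3 randomises cohorts of 10 to 18 at a site. If Burlington supplied exactly one such cohort out of 184, *f* would be 10/184 = 5.4% to 18/184 = 9.8%. The number of Burlington cohorts is an assumption.

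**The case against.** The strongest reply is that the safety plan does not rest on this sentence. Section 6.3 C, just before it, collects information through calls, conversations with clinic staff and group sessions without limiting any of these to particular clinics. Participants also sign a release allowing their clinic to give information to the study team (4.6 B), with no clinic excluded. This stands, and it rules out a reading that the omission might invite, namely that Burlington events between visits depend only on what participants recall at weeks 8 and 16.

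A second reply is that Burlington shares leadership with NBCC and may be covered through it. The documents neither say so nor rule it out. Section 2.2 mentions the leadership but does not say that NBCC staff would learn of, or report, events among Burlington participants.

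A third is that this is a drafting slip. The same three names in 4.5 E support that, and they also show that Burlington is not listed in every recruitment passage. A reader might infer that Burlington was deliberately left out of safety reporting, and nothing in the documents supports that. A slip in an operative instruction still matters, because staff would follow it as written.

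Finally, randomisation within site means that a clinic-level gap does not by itself bias the comparison between arms. That is right. The possible imbalance arises only because one of the remaining routes exists in one arm.

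**Conclusion.** The point holds as a gap in one reporting route at one clinic. One of four recruiting organisations is outside the standing request in 6.3 D, so adverse-event capture may be less complete there, chiefly for TAU participants and those who cannot be reached. Its size cannot be determined from the documents.

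A reader might go further and conclude that the DSMB's totals are incomplete. The documents do not support that as a fact: the routes in 6.3 C may pick up every Burlington event, and Burlington staff may have been asked in practice. No efficacy outcome depends on this sentence, and section 4.9 describes risks as minimal. The conclusion assumes that 6.3 D is carried out as written and that the request to NBCC does not extend to Burlington. If it does extend, the text needs only to say so.

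**What to change.** Reword 6.3 D so that the request goes to personnel at 'all participating clinics, including any added later'. The open wording is better than adding one name, because 4.5 E allows further sites to join and a fixed list would go out of date again. Reconcile the site lists in 4.5 E and 6.3 D with those in 1.3 and 4.2.

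The cost is one wording change and one more notification request. The release in 4.6 B already allows a participant's clinic to give information to the study team, so no new kind of consent appears to be needed. If Burlington has already enrolled participants, the investigators should also confirm whether its staff were asked to report.
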